
propensity score matched cohort, Cox regression will be used to estimate the hazard ratios and 95% CI for Tiotropium/Olodaterol compared to patients treated with Tiotropium during follow-up for time-to-first triple therapy initiation using an intention-to-treat censoring approach.
 
Sensitivity Analyses
 
 1. Less Stringent Qualifying Event Criterion 
Instead of defining the qualifying event as two prescriptions within 60 days, patients may enter on only one prescription. While some confidence is lost in whether the patients truly took their index medications, the less stringent qualifying event criterion will allow more patients to be included, increasing statistical power. Furthermore, the possibility of immortal time bias is also mitigated, since the time between prescriptions is no longer present.
 
 2. As-treated Censoring 
The analysis will use an as-treated approach for primary, secondary and further endpoint outcomes. In addition to the censoring criteria mentioned for the intention-to-treat approach (outcome, death, or end of data), patients will also be censored after medication discontinuation or switching over to the other arm.
 
 3. Alternative algorithm for COPD as exclusion criterion 
The analysis will use a different set of diagnosis codes for COPD (J43*, J44*) to identify patients with COPD. Compared to the primary analysis, this identification approach omits the diagnostic code for chronic bronchitis (J41*), as this code is commonly used by pulmonologists when prescribing Mucolytics to patients without
			

Name of company: Boehringer Ingelheim			
Name of finished medicinal product: Spiolto® Respimat®; Spiriva® Respimat®			
Name of active ingredient: Tiotropium / Olodaterol fixed dose combination (ATC R03AL06); Tiotropium (ATC R03BB04)			
Protocol date: 27 Feb 2020	Study number: 1237.100	Version/Revision: 1.0	Version/Revision date: N/A

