Patients with uncontrolled COPD experiencing exacerbations may escalate to triple LAMA/LABA/ Inhaled Corticosteroids (ICS) therapy (**Vogelmeier 2017**). According to prior COPD guidelines, ICS can be used for frequent exacerbations, but the most recent GOLD guidelines recommend that ICS only be used for Asthma-COPD-overlap patients (**Vogelmeier 2017**). However, in the DYNAGITO study, the prevalence of LAMA/LABA/ICS (triple therapy) at baseline was 40.8% in moderate to very severe COPD patients in Japan (**Calverley 2018, Ichinose 2018**). ICSs may lead to several minor and major complications. The side effects of ICS treatment can range from weight gain and local side effects, such as pneumonia, oral candidiasis and dysphonia, to adrenal suppression, cataracts, and osteoporosis (**Tariq 2016, Wilkie 2015**). In addition, patients with low blood eosinophil counts may not respond to ICS (**Hizawa 2015**).

Several clinical trials have shown that new LAMA/LABA inhalers could better manage patients, potentially reducing the use of ICS as part and parcel of maintenance therapy in COPD (**Magnussen 2014**). However, the evidence obtained from previous clinical trials is not always reflected in clinical practice, and there is limited research from real world settings

that show LAMA+LABA combination therapy provides more benefit than LAMA monotherapy in Japanese patients with COPD. Therefore, real world evidence from Japanese COPD patients is crucial in addressing this gap in knowledge. It is also essential to understand real world treatment patterns and outcomes, in particular, escalation to triple therapy as a proxy for worsening COPD condition.

Spiolto® Respimat®, a combination of Olodaterol (a LABA) and Tiotropium (a LAMA) (herein referred to as Tio/Olo) was approved in September 2015 in Japan. Spiriva® Respimat®, a Tiotropium (a LAMA) monotherapy (herein referred to as Tio), was approved in October 2004 and widely used in Japan. Both maintenance therapies are available, but real world evidence is lacking if one therapy is superior to the other, and whether it can prolong the duration to triple therapy that includes ICS.

This study aims to evaluate the time to escalation to triple therapy among the Japanese COPD patients newly initiating therapy with Tio or Tio/Olo using real world data.

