9.2 SETTING

9.2.1 Definitions

Study Period: the entire period of time that includes the baseline period, the cohort entry date (index date), and follow-up period for the study population. The study period will be from **01 April 2015** (180 days prior to Spiolto approval date of 28 September 2015 in Japan) to **31 March 2019** (end of available data).

Patient Selection Period: the period of time for which patients are eligible to enter the cohort. The earliest date of the patient selection period is **28 September 2015**, (the Spiolto approval date in Japan). The latest date of the patient selection period is 31 December 2018, corresponding to 90 days before the end of available data (31 March 2019), ensuring that all patients have at least 60 days after the cohort entry date to identify a second prescription for index therapy and at least 30 days to be capable of the 30-day overlap to determine the triple therapy initiation outcome.

Cohort Entry Date: Date of entry to the initial cohort of Tio/Olo vs. Tio users (*first prescription*).

Baseline Period: the 180-day period that ends 1 day prior to the cohort entry date used to assess covariate information. The earliest start of the baseline period would be 01 April 2015, corresponding to 180 days prior to the approval date of Spiolto.

[figure not shown]
Follow-Up Period: the period starting at the second prescription for Tio/Olo or Tio within 60 days of the cohort entry date (first prescription) and ending at the earliest occurrence of the outcome (use of triple therapy), or the first occurrence of inpatient death, disenrollment, or end of the study period (31-Mar-2019). A sensitivity analysis will employ an as-treated censoring approach to further censor upon discontinuation of index therapy or initiation of the other index treatment arm. Patients may have different lengths of follow-up (i.e. variable follow-up).

Since health care is nationalized in Japan, the notion of enrollment is not applicable. Therefore, a proxy enrolment criterion defined as start of enrolment = date of first inpatient/outpatient encounter; end of enrolment = date of last inpatient/outpatient encounter will be used. “Enrolment” herein will refer to this proxy enrolment measure. For entry into the study population, patients will be required to have had at least 180 days of enrollment prior to the cohort entry date.

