9.3.2 Outcomes

9.3.2.1 Primary outcomes

Triple Therapy Use

[figure not shown]
The primary outcome of interest is incident rate of triple therapy initiation (first event per patient) defined as any LAMA/LABA/ICS fixed dose combination or any concurrent use for 30 consecutive days of the following:

- any LAMA/LABA fixed dose combination + any ICS single formulation
- any LAMA single formulation + any LABA/ICS fixed dose combination
- any LAMA single formulation + any LABA single formulation + any ICS single formulation

MDV data has limited information on treatment duration with the days of prescription recorded as 1 day for most patients. Therefore, a days supply of 30 days will be assumed. Although we will require at least 30 days of overlap, the first date of triple therapy overlap will serve as the outcome event date, as corresponds to the initiation of triple therapy. Looking into the future to satisfy the requirement of overlap for at least 30 days has the potential to inflict immortal person-time, but is necessary to differentiate concurrent use when subsequent medication is added (see [Figure 3](#) - example Patient A) from an early sequential prescription fill when subsequent medication is switched to (see [Figure 3](#) - example Patient B).

Figure 3

Illustration of outcome

Censoring

Patients will be censored if they had an occurrence of any of the following: outcome (initiation of triple therapy), death, or end of data. The analysis will use an intention-to-treat censoring approach, which does not account for treatment change. A sensitivity analysis will employ an as-treated censoring approach to further censor upon discontinuation of index therapy or initiation of the other index treatment arm. Thus, events will be assigned to exposure groups according to that patient's original index medication, even if that patient discontinued or crossed over.

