9.7.1.3 Comparative Effectiveness

● *Hazard Ratio for Triple Therapy Use Initiation*

Among both the basic propensity score matched and high dimensional propensity score matched cohort, Cox regression will be used to estimate the hazard ratios and 95% CI for Tiotropium/Olodenaterol compared to patients treated with Tiotropium during follow-up for time-to-first triple therapy initiation using an intention-to-treat censoring approach.

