9.9 LIMITATIONS OF THE RESEARCH METHODS

This study will be conducted using hospital-based health insurance claims following the DPC payment system and is subject to certain limitations. One limitation is that these are based on a large, non-random convenience sample based in Japan, which may contain biases or lack generalizability to other populations. Data also come from a subset of hospitals in Japan, which would lead to failure to record events if patients visit medical centers not included in MDV's data sources (**Tanaka 2015**). Moreover, because healthcare is nationalized in Japan, the notion of enrolment is not applicable, and all patients are assumed to be observable throughout the global date range of the data. However, if a patient's emigration or mortality is not captured, then they would remain in the study despite not truly being eligible for any events, thereby leading underestimations of the risks and rates and possible bias in the hazard ratio if these patients are differentially distributed between the exposed and unexposed groups.

Another limitation of the study is that patients on monotherapy may escalate to double therapy before receiving the triple therapy. The patients starting on double therapy do not have this option. Therefore, patients on monotherapy may take longer to get to triple therapy than the patients on double therapy.

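### The comparative result is one time-constant Cox hazard ratio per matched cohort; proportional hazards are doubtful on the plan's own account, and no check or fixed-horizon measure is planned

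*Combined protocol and SAP*

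**What the plan says.** The data-analysis part of the abstract (Section 4) states: "Cox regression will be used to estimate the hazard ratios and 95% CI for Tiotropium/Olodaterol compared to patients treated with Tiotropium during follow-up". Section 9.7.1.3 repeats this for both the basic and the high-dimensional propensity score matched cohorts: "Cox regression will be used to estimate the hazard ratios and 95% CI", with intention-to-treat censoring. Section 9.7.1.2 adds crude rates (events per person-year) and crude risks (events divided by patients at risk), each as a ratio and a difference. The risk has no time horizon.

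Neither the abstract nor Section 9.7 mentions a proportional-hazards check, period-specific HRs, a Kaplan-Meier or other fixed-time risk, or restricted mean time.

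The question in Section 7 is about time: whether one therapy is superior, and "whether it can prolong the duration to triple therapy that includes ICS".

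Section 9.9 lists as a limitation that "patients on monotherapy may escalate to double therapy before receiving the triple therapy. The patients starting on double therapy do not have this option", and concludes that "patients on monotherapy may take longer to get to triple therapy than the patients on double therapy". It does not connect this to the Cox model. Section 9.3.2.1 also counts a one-step move from Tio as the event: "any LAMA single formulation + any LABA/ICS fixed dose combination".

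The end of follow-up is described in three ways. Section 9.2.1 and the note to Figure 1 include disenrollment, by a proxy based on the last encounter. The censoring paragraph in Section 9.3.2.1 lists outcome, death and end of data only. Section 9.9 assumes that all patients are observable across the whole date range of the data.

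**The concern.** A Cox HR is a single number for the whole of follow-up. If the true HR is constant, the mix of short and long follow-up does not matter. If it changes, the estimate is an average over event times, and censoring decides which times count. Two analysts with the same patients but different rules for ending follow-up could then report different HRs for the same effect.

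The plan itself gives a reason to doubt constancy. A Tio patient can reach triple therapy directly or through double therapy, and the mix of patients on one or two drugs shifts with time. A Tio/Olo patient is already on two drugs.

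Three things are at stake: the meaning of the headline HR, the comparison of the primary analysis with sensitivity analyses that have shorter follow-up, and whether anything reported answers the Section 7 question about prolonging the time to triple therapy.

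**Working it through.** **The plan's own figures (Section 9.5).** The inputs are 1-year risks of 6% (Tio/Olo) and 10% (Tio), HR 1.73, two-sided alpha 0.05, 90% power and 1:1 allocation.
- Events = 4(1.960 + 1.282)² / ln(1.73)² = 139.9, so 140 against the stated 141. This reproduces.
- Constant hazards from the risks are −ln(0.94) = 0.0619 and −ln(0.90) = 0.1054 per year. The HR is 0.0619/0.1054 = 0.587 for Tio/Olo versus Tio, or 1.703 the other way round. Section 9.5 states 1.73 and the abstract 1.7.
- At 1.703, 149 events are needed, and 149/0.08 = 1862 patients against the stated 1856.

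The planning is thus consistent with a constant HR near 0.59.

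**Follow-up range.** From 28 September 2015 to 31 March 2019 is 1280 days, or 3.5 years from cohort entry. From the last allowed start, 1 March 2019, to 31 March 2019 is 30 days.

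**Three-state model for Tio.** Let a be the yearly rate from mono to triple therapy, b from mono to double, and c from double to triple. The documents give none of these, so all values are assumptions. Tio/Olo has a constant hazard of 0.0619, there is no competing death, and each case is calibrated so that the 1-year Tio risk is 10%.
- Mono(t) = exp(−(a+b)t)
- Double(t) = b/(a+b−c) × [exp(−ct) − exp(−(a+b)t)]
- HR(t) = 0.0619 × [Mono + Double] / [a·Mono + c·Double]

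Given b > 0, HR(t) is constant only if a = c. Example with b = 0.5, c = 4 × 0.0619 = 0.2475 and a = 0.0689: Mono(1) = 0.566 and Double(1) = 0.334, so the risk is 1 − 0.900 = 10%. HR(0) = 0.0619/0.0689 = 0.90. HR(1) = 0.0557/(0.0390 + 0.0826) = 0.46.

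The large-sample Cox HR θ solves ∫[S₁h₁ − θS₁/(θS₁+S₀) × (S₁h₁+S₀h₀)]·G dt = 0, where S and h are survival and hazard (1 = Tio/Olo, 0 = Tio) and G is the share still uncensored.

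| b | c ÷ 0.0619 | a (solved) | all 0.5 y | all 1 y | all 2 y | all 3.5 y | uniform 0.25–3.5 y | same, 30% lost per year |
|---|---|---|---|---|---|---|---|---|
| any | c = a | 0.105 | 0.59 | 0.59 | 0.59 | 0.59 | 0.59 | 0.59 |
| 0.3 | 1.5 | 0.107 | 0.58 | 0.59 | 0.60 | 0.61 | 0.60 | 0.59 |
| 0.5 | 1 | 0.117 | 0.56 | 0.59 | 0.64 | 0.70 | 0.65 | 0.63 |
| 0.5 | 2 | 0.100 | 0.60 | 0.59 | 0.57 | 0.55 | 0.57 | 0.57 |
| 0.5 | 4 | 0.069 | 0.70 | 0.59 | 0.48 | 0.40 | 0.47 | 0.50 |
| 1.0 | 4.9 | 0 (strict two-step) | 1.00 | 0.59 | 0.39 | 0.31 | 0.38 | 0.43 |

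The 1-year risks are 6% and 10% in every row, a difference of 4.0 points. The Cox HR equals the planning value only when follow-up is about 1 year. The last two columns show how counting disenrollment can move it (0.47 to 0.50 and 0.38 to 0.43 in the steeper cases, little in the others).

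**Limit on the strict route.** With a = 0 and c equal to the Tio/Olo hazard, the 1-year Tio risk is only 0.6% (b = 0.2) to 5.9% (b = 50). So the plan's 10% requires either a real direct route or a higher hazard after double therapy.

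**The other planned measures.** The risk is events over patients with unequal follow-up, so it grows with follow-up. The rate ratio is a ratio of averages over person-time and shifts with follow-up unless the ratio of hazards is constant. Neither fills the gap.

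**The case against.** Section 9.9 says only that patients may step up; it gives no rate. Section 9.3.2.1 counts direct escalation from Tio. If that route dominates, or if the hazard after double therapy is close to the direct one, the HR is nearly constant and the Cox estimate is a fair summary. The matching includes calendar year of entry, so administrative follow-up should be similar in the two arms. Power is not at issue: at 1 year every scenario gives 1856 × 0.08 = 148 events. All of this stands. None of it shows that proportional hazards hold, and balanced follow-up does not stop the average from depending on its length.

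A reader might infer more than the documents support:
- *That the HR must change, and must fall.* The table has a flat case and a rising case under the same 6% and 10%.
- *That the drift is very large, for example 0.85 at 6 months to 0.32 at 3.5 years.* This arises with a = 0.03 and b = 0.3 to 0.6, but c is then 0.69 to 0.36 per year, which is 11 to 6 times the Tio/Olo hazard. Across a = 0 to 0.06 with the same b, the ratio is 16 to 4. Nothing in the plan supports such values.
- *That the as-treated analysis would move toward 1 because it is shorter.* When c equals the Tio/Olo hazard, shorter follow-up moves the HR away from 1 (0.70 at 3.5 years, 0.56 at 6 months). As-treated censoring also stops a Tio patient at the start of Tio/Olo, which removes part of the two-step route, so length is not the only thing that changes.

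**Conclusion.** The point holds in a conditional form. The plan names a mechanism that makes proportional hazards doubtful, allows follow-up from about 30 days to 3.5 years with conflicting end rules, and plans neither a check nor a summary at a fixed time. If proportionality fails, the reported HR depends on follow-up and does not by itself say how far triple therapy is delayed.

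Size and direction cannot be determined from the documents. Between 6 months and 3.5 years of follow-up, the Cox HR could be almost constant (0.58 to 0.61), rise from 0.56 to 0.70, or fall from 0.70 to 0.40, and further if the hazard after double therapy is very high. These ranges rest on assumed transition rates, constant rates within each state, a constant Tio/Olo hazard and no competing death. This is a cheap improvement in interpretation; it does not invalidate the Cox analysis.

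**What to change.** In Sections 9.7.1.2 and 9.7.1.3, and in the matching abstract text:

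1. Keep the Cox HR as the primary estimate.
2. Pre-specify beside it, in each matched cohort and with 95% CIs, the 1-year difference in cumulative incidence of triple therapy (Kaplan-Meier, or competing-risk with death) and/or in restricted mean time free of triple therapy. One year is the horizon of the study-size assumption. Let this replace the events-over-patients risk.
3. Add a proportional-hazards assessment (log-log plots, scaled Schoenfeld residuals), with period-specific HRs as supportive description. Do not let the result of that assessment switch the primary measure.
4. Report the sensitivity analyses at the same 1-year horizon.
5. Use one definition of end of follow-up in Sections 9.2.1, 9.3.2.1 and 9.9.

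The cost is wording and a few more runs on the same matched data. The downside is that more than one number describes the primary effect. The restricted mean difference will also look small: under constant hazards it is 0.06/0.0619 − 0.10/0.1054 = 0.970 − 0.949 = 0.021 years, about 7.5 days, so the risk difference may be easier to read. Fixed-horizon estimates still assume uninformative censoring, which is a further reason to settle item 5.

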5. AMENDMENTS AND UPDATES

Number	Date	Section of study protocol	Amendment or update	Reason
<1>	DD Month YYYY	<Text>	<Text>	<Text>
<2>	DD Month YYYY	<Text>	<Text>	<Text>
<n>	DD Month YYYY	<Text>	<Text>	<Text>

6. MILESTONES

7. RATIONALE AND BACKGROUND

Chronic obstructive pulmonary disease (COPD) is a common disease characterized by airway obstruction confirmed by spirometry, often including small airway obstruction, chronic bronchitis, and emphysema (**Barnes 2015**). It is a leading cause of death in the USA, affecting 16 million Americans (National Heart Lung and Blood Institute, USA). The prevalence of COPD in Japan is about 8.6% (**Fukuchi 2004**), costing approximately ¥805.5 billion (US\$6.8 billion) per year (**Nishimura 2004**).

No known medications can reverse COPD, but regular maintenance treatments can help manage symptoms, reduce the frequency of exacerbations, and improve health-related quality of life (**Braido 2016**). Bronchodilators have been the cornerstone of COPD disease management and are prescribed as first-line therapy for patients with COPD. According to the 2017 GOLD guidelines, a long-acting muscarinic antagonist (LAMA) or long-acting beta agonist (LABA) is recommended as the first line treatment in GOLD B, followed by combination therapy LAMA + LABA if the COPD patients are still symptomatic in GOLD D. Several studies have found LAMA+LABA combinations to be more effective than their mono-components and without minimal increase in adverse events. In a review study, Mosely et al. reported that the combination of tiotropium and olodaterol hydrochloride is more effective at improving FEV1 than either of the two agents used alone (**Mosely 2016**). Singh et al., in a phase III trial, found patients receiving tiotropium and olodaterol responded better than those receiving tiotropium monotherapy, and conclude that tiotropium + olodaterol should be considered as a treatment option in patients with moderate COPD who are initiating maintenance therapy (**Singh 2016**). Other clinical trials, such as Tonado 1 and Tonado 2, have also shown that tiotropium/olodaterol fixed-dose combination (FDC) therapy provides significantly improved lung function and quality of life, compared with either therapy used individually in COPD (**Buhl 2015, Ichinose 2016**). In addition, recent clinical trials have found tiotropium/olodaterol FDC therapy significantly improved exercise capacity, and physical activity compared with tiotropium monotherapy. (**Minakata 2019, Ichinose 2018**)

Patients with uncontrolled COPD experiencing exacerbations may escalate to triple LAMA/LABA/ Inhaled Corticosteroids (ICS) therapy (**Vogelmeier 2017**). According to prior COPD guidelines, ICS can be used for frequent exacerbations, but the most recent GOLD guidelines recommend that ICS only be used for Asthma-COPD-overlap patients (**Vogelmeier 2017**). However, in the DYNAGITO study, the prevalence of LAMA/LABA/ICS (triple therapy) at baseline was 40.8% in moderate to very severe COPD patients in Japan (**Calverley 2018, Ichinose 2018**). ICSs may lead to several minor and major complications. The side effects of ICS treatment can range from weight gain and local side effects, such as pneumonia, oral candidiasis and dysphonia, to adrenal suppression, cataracts, and osteoporosis (**Tariq 2016, Wilkie 2015**). In addition, patients with low blood eosinophil counts may not respond to ICS (**Hizawa 2015**).

Several clinical trials have shown that new LAMA/LABA inhalers could better manage patients, potentially reducing the use of ICS as part and parcel of maintenance therapy in COPD (**Magnussen 2014**). However, the evidence obtained from previous clinical trials is not always reflected in clinical practice, and there is limited research from real world settings

that show LAMA+LABA combination therapy provides more benefit than LAMA monotherapy in Japanese patients with COPD. Therefore, real world evidence from Japanese COPD patients is crucial in addressing this gap in knowledge. It is also essential to understand real world treatment patterns and outcomes, in particular, escalation to triple therapy as a proxy for worsening COPD condition.

Spiolto® Respimat®, a combination of Olodaterol (a LABA) and Tiotropium (a LAMA) (herein referred to as Tio/Olo) was approved in September 2015 in Japan. Spiriva® Respimat®, a Tiotropium (a LAMA) monotherapy (herein referred to as Tio), was approved in October 2004 and widely used in Japan. Both maintenance therapies are available, but real world evidence is lacking if one therapy is superior to the other, and whether it can prolong the duration to triple therapy that includes ICS.

This study aims to evaluate the time to escalation to triple therapy among the Japanese COPD patients newly initiating therapy with Tio or Tio/Olo using real world data.

